16.7 Inclusion of Women and Minorities

- 16.71 This study will be available to all eligible patients, regardless of race, gender, or ethnic origin.
- 16.72 There is no information currently available regarding differential effects of this treatment regimen in subsets defined by race, gender, or ethnicity, and there is no reason to expect such differences to exist. Therefore, although the planned analysis will, as always, look for differences in treatment effect based on racial and gender groupings, the sample size is not increased in order to provide additional power for subset analyses.
- 16.73 Based on prior MCCC studies involving similar disease sites, we expect about 4% of patients will be classified as minorities by race and 40% of patients will be women. Expected sizes of racial by gender subsets are shown in the following table:

Accrual Estimates by Gender/Ethnicity/Race for All Phase 2 and 3 Studies

| Ethnic Category | Sex/Gender | | | | | | |
|--|------------|-------|---------|-------|--|--|--|
| , | Females | Males | Unknown | Total | | | |
| Hispanic or Latino | 1 | 2 | | 3 | | | |
| Not Hispanic or Latino | 18 | 26 | | 44 | | | |
| Ethnic Category: Total of all subjects* | 19 | 28 | | 47 | | | |
| Racial Category | | | | | | | |
| American Indian or Alaska Native | 0 | 1 | | 1 | | | |
| Asian | 0 | 0 | | 0 | | | |
| Black or African American | 1 | 1 | | 2 | | | |
| Native Hawaiian or other Pacific Islander | 0 | 0 | | 0 | | | |
| White | 18 | 26 | | 44 | | | |
| Racial Category: Total of all subjects* | 19 | 28 | | 47 | | | |

Ethnic Categories:

Hispanic or Latino – a person of Cuban, Mexican, Puerto Rico, South or Central American, or other Spanish culture or origin, regardless of race. The term "Spanish origin" can also be used in addition to "Hispanic or Latino."

Not Hispanic or Latino

Racial Categories:

American Indian or Alaska Native – a person having origins in any of the original peoples of North, Central, or South America, and who maintains tribal affiliations or community attachment.

Asian – a person having origins in any of the original peoples of the Far East, Southeast Asia, or the Indian subcontinent including, for example, Cambodia, China, India, Japan, Korea, Malaysia, Pakistan, the Philippine Islands, Thailand, and Vietnam. (Note: Individuals from the Philippine Islands have been recorded as Pacific Islanders in previous data collection strategies.)

Black or African American – a person having origins in any of the black racial groups of Africa. Terms such as "Haitian" or "Negro" can be used in addition to "Black or African American."

Native Hawaiian or other Pacific Islander – a person having origins in any of the original peoples of Hawaii, Guam, Samoa, or other Pacific Islands.

White – a person having origins in any of the original peoples of Europe, the Middle East, or North Africa.

17.0 Pathology Considerations/Tissue Biospecimens

17.1 Summary Table of Research Tissue Specimens to be Collected for this Protocol

| Correlative Study (Section for more information) | Mandator y or Optional | Block, Slides, Core, etc. (# of each to submit) | Baseline | At disease progres sion | Process at site? (Yes or No) | Temperatur e Conditions for Storage /Shipping |
|--|------------------------------|---|----------|----------------------------------|---------------------------------------|---|
| Archival Tissue - | Mandatory | FFPE Blocks or Slides ¹ | X^2 | | No | Ambient/ Ambient |
| Tissue - | Optional | FFPE Blocks or Slides ¹ | | X³ | No | Ambient/ Ambient |

- 1. Formalin Fixed Paraffin Embedded (FFPE). If a block is not available, then please submit 1 H&E and 10 unstained slides
- 2. Submit Pathology report with archival tissue sent to the MCF Biospecimen Facility.
- 3. For those subjects in Event Monitoring for reasons other than PD (e.g. adverse event, refusal), optional tissue will not be collected

17.2 Tissue Collection and Processing

Tissue will be obtained from previous biopsy material or from biopsy of accessible tumor sites at protocol entry, along with pathology report. Patients who consent and who have accessible disease will have tissue samples obtained by standard needle core biopsy at the time of disease progression as well. These samples will be analyzed by [name] as described in Section 17.3.

Forward FFPE tissue to the following laboratory: [name] Pathology Research Core Mayo Biorepositories [name]

For quality assurance purposes, biopsy tissues will be fixed immediately in 10% phosphate-buffered formalin and fixed tissues will be embedded in paraffin. Tissue processing will occur at the BAP/PRC Laboratory, which is a College of American Pathologists (CAP) certified

This laboratory follows the NCI guidelines (National Cancer Institute Best Practices for Biospecimen Resources, 2007) and develops customized Quality Assurance/Quality Control (QA/QC) policies and procedures for each study. In

this particular study, the quality of biopsy tissues will be assessed by the study pathologist ([name]) on an H&E slide. For patients who have previously undergone biopsy, existing biopsy tissue may be used.

Samples upon arrival will be accessioned into the biorepository through the Research Laboratory Information Management System (RLIMS), samples are to be forwarded to [name] laboratory in Griffin Building in MCF.

17.3 Background

Genomic DNA will be extracted from 5-3 μ m sections from the biopsy and subjected to *PRKCI* gene copy number analysis as described previously. Sections (3 μ m) from the biopsy will be processed for IHC using established protocols as described previously.

Tissue sections will be stained with antibodies specific to PKC1, phospho-Ser298-Mek, phospho-Thr202/Tyr204-Erk, phospho-Ser473-Akt, phospho-Thr70-4E-BP1 and phospho-Ser240/244-S6 (Cell Signaling Technology Inc.) as previously described.

Expression of these markers will be evaluated as described below for correlation with response to Auranofin/Sirolimus therapy with the primary clinical endpoint being progression free survival.

Standardization of IHC scoring: A drawback of IHC staining for detection and quantification of biomarkers is the inherent variability in IHC staining from analysis to analysis and from sample to sample. We will minimize this variability by constructing a "standard curve" of staining intensity on a scale from 0 to +3 for each of the potential biomarkers using well-characterized archival primary NSCLC tumor tissues. We have already constructed such a standard curve TMA for PKC1 as follows: First, we performed immunohistochemical analysis for PKC1 on 4 tissue microarrays (TMAs) containing ~100 well-characterized archived primary NSCLC cases. Each of the 100 samples were scored on a 0 to+3 scale based on PKC1 staining intensity by our board certified lung pathologist, [name]. A 0 score corresponds to tumor PKC staining equivalent to the surrounding stroma, and scores of +1, +2 and +3 correspond to increasing intensity of PKC1 staining in the tumor specimen compared to the surrounding stroma.

Tissue blocks from cases corresponding to each numerical value on the intensity scale were retrieved and used to construct a new TMA. This "standard curve" TMA contains 4 NSCLC cases that exhibit a gradient of PKCı staining representative of the full range of staining intensity across the original 100 samples (*Figure 1*). The standard curve will be validated by a second pathologist ([name]). For our proposed analysis, tissue sections from each enrolled patient will be subjected to IHC for PKCı in parallel with a section from this "standard curve" TMA. The sections will be analyzed at the same time using the same reagents and protocol to ensure uniformity of scoring across samples. Each experimental sample will be assigned a score, based on the standard curve on a 0 to +3 scale, by two pathologists independently with joint review and resolution of discrepancies as necessary. Additionally, image analysis will be performed using ImageScope and associated image quantification software.

A similar approach will be used to generate "standard curve" TMAs for each of the potential predictors of response, phospho-Ser 298-Mek, phospho-Thr202/Tyr204-Erk, phospho-Ser473-Akt, phospho-Thr70-4E-BP1 and phospho-Ser240/244-S6. IHC scoring criteria and interpretation will be guided by published reports evaluating these markers in NSCLC cases, and will take into account, as appropriate, not only staining intensity, but also percent of tumor cells stained positively and nuclear versus cytoplasmic distribution of phosphoantigens. Phospho-Erk scoring will follow the criteria established by Cappuzzo et al. Specifically, sections will be scored on the following scale: 0=no tumor cells stain positively; +1= more than 10% of the tumor cells stained weakly; +2= more than 10% of the tumor cells stained moderately; and +3=more than 10% of the tumor cells stained strongly. Phospho-Akt staining will be evaluated based on the criteria established by David et al. Scoring will be on the following scale: 0=no staining in tumor cells; +1=slightly elevated staining in cytoplasm and/or nucleus as compared with stromal elements; +2=moderate staining in tumor cell cytoplasm and/or nucleus; and +3=dark staining in tumor cells completely obscuring cytoplasm and/or nucleus.

Phospho-S6 staining will be scored using the criteria established by Conde et al. Specifically, samples will be scored for staining intensity as follows: 0=no tumor staining; +1=weak cytoplasmic staining; +2=moderate cytoplasmic staining; and +3=strong cytoplasmic staining. Extent of staining will also be scored according to the percentage of tumor cells that stain positively for antigen as follows: 0=0% of cells staining; +1= \leq 50% staining; +2= \leq 51-75% cells staining; +3= \leq 76-85% cells staining; and +4=>85% cells staining. The sum of the intensity and extent of scoring will be used as the final staining score (0-7). In their study, Conde et al. considered tumors with a final score of ≥ 5 as being positive or high-intensity, whereas those with a final score of <5 were negative or low-intensity. This binary model will be considered in our patient sample as described below. No scoring scale has been published for phospho-Ser298- Mek or 4E-BP1 staining in primary NSCLC tumors. However, we will consider the criteria established by Akcakanat et al. for analysis of 4E-BP1 immunohistochemical staining in primary breast cancer tumors. We will establish such interpretation criteria based on the staining patterns exhibited by our analysis of the TMA containing our 100 archival NSCLC cases. Staining intensity, percent positive cells, staining relative to surrounding stroma and nuclear/cytoplasmic distribution will be considered as potential criteria in devising standard curve TMAs and scoring paradigms for these antigens. Data from IHC scoring will be analyzed for correlation with clinical response using standard statistical treatments by our staff statistician. Specifically, the association of the endpoint of PFS at 4 months with the predictor variables PRKCI gene copy number (presence of ≥ 1 extra copy of the gene) and IHC scoring for the given marker will be evaluated using logistic regression models, where an odds ratio and 95% confidence interval will be estimated. A separate logistic regression model will be utilized for each predictor variable. For each marker, IHC scores will be considered as a numerical variable to assess

evidence of a linear association, and also as a binary categorical variable based on the sample median IHC score for the given marker. Given availability of information regarding PFS beyond the time point of interest of 4 months, in exploratory analyses, associations of the aforementioned predictor variables with PFS at any time point will be evaluated using the Kaplan-Meier method and Cox proportional hazards models (censoring at the date of last follow-up), which will account for the varying lengths of follow-up between patients. Diagnostic Slides from Original and /or Recurrent Tissue.

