1.2 Protein Kinase Ct is a Novel Target

1.21 Protein Kinase Ct is an oncogene that can mediate K-ras induced lung carcinogenesis. The protein kinase C (PKC) family of serine/threonine kinases has been implicated in many forms of cancer, including lung cancer, and is therefore a potential therapeutic target for cancer treatment.

We recently demonstrated that the atypical protein kinase C, PKCı, is an oncogene in non-small cell lung cancer (NSCLC) {Regala, 2005 #50}. PKCı is overexpressed in NSCLC and SCLC tumors and tumor PKCı expression is predictive of poor clinical outcome independent of tumor stage {Regala, 2005 #50 & personal communication, [name]}. The PKCı gene is a target of frequent, tumor-specific alteration by gene

amplification in a significant subset of NSCLCs {Stallings-Mann, 2006 #49}. Genetic disruption of PKCı signaling blocks the transformed growth of NSCLC cells in vitro and in vivo {Regala, 2005 #51}. Oncogenic PKCı signaling requires the N-terminal PB1 domain on PKCı {Stallings-Mann, 2006 #49}.

Using a high throughput screen, we identified the anti-arthritic gold salt aurothiomalate (ATM) and subsequently a similarly acting oral agent, Auranofin (Ridaura), as potent inhibitors of oncogenic PKCı signaling. ATM and auranofin both inhibit transformed growth of NSCLC cells by binding to the PB1 domain of PKCı, and blocking the interaction between PKCı and downstream adaptor molecules {Erdogan, 2006 #52}.

These agents exhibit potent anti-tumor activity against NSCLC in vitro and in vivo. We have demonstrated a correlation between the sensitivity of NSCLC cells to the anti-tumor effects of ATM, and the level of expression of PKC1. NSCLC cells that express high levels of PKC1 are more sensitive to ATM than those with relatively low levels of PKC1 expression. A phase I clinical trial conducted at our institution demonstrated feasibility of the approach. Because of drug shortages, we were unable to obtain ATM for the clinical trial described here. We therefore tested the oral, similarly acting agent auranofin in the laboratory. This drug is FDA approved for arthritis with the same indications as ATM. In vitro, its activity is at least equal to that of ATM at concentrations mirroring those found in human serum with standard clinical use. We hypothesize that auranofin will be an effective therapy for the treatment of NSCLC, especially those subsets of NSCLC exhibiting PKC1 over-expression.

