16.52 Definitions and Analyses of Secondary, Exploratory, and Correlative Endpoints

Survival time is defined as the time from registration to death due to any cause. The distribution of survival time will be estimated using the method of Kaplan-Meier (1958).

Progression-free survival time is defined as the time from registration to the earliest date of documentation of disease progression. If a patient dies without a documentation of disease progression the patient will be considered to have had disease progression at the time of their death. In the case of a patient starting treatment and then never returning for any evaluations, the patient will be censored for progression 1 day post-registration. The distribution of progression-free survival time will be estimated using the method of Kaplan-Meier (1958).

A response is defined to be either a CR or PR noted as the objective status. As response rate is a secondary endpoint, confirmation is no longer required per RECIST v1.1. The overall response rate will be estimated in the subset of patients with measureable disease by the number of responses in evaluable patients with measurable disease divided by the total number of evaluable patients with measureable disease. The appropriate confidence interval will be calculated based on the binomial distribution.

Duration of response is defined for all evaluable patients with measurable disease who have achieved a response as the date at which the patient's earliest best objective status is first noted to be either a CR or PR to the earliest date progression is documented. If a patient dies subsequent to the response without a documentation of disease progression, the patient will be considered to have had disease progression at the time of their death. In the case of a patient failing to return for evaluations before a documentation of disease progression, the patient will be censored for progression on day 1 post response or the date of last evaluation (whichever one occurs later). The distribution of

duration of response will be estimated using the method of Kaplan-Meier (1958).

Translational analyses: Given the small sample size, all translational analyses are considered exploratory and no adjustment for multiplicity will be employed. One-sided p-values

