≤0.10 are considered statistically significant throughout. Results will be used to design subsequent confirmatory studies (likely as translational components within the subsequent phase III study should this phase II study support the use of this combination in a phase III study).

We consider the analysis of baseline PKCı gene amplification to be the primary analysis (though still exploratory) among the

various translational anlayses. PKCı gene amplification will be evaluated at baseline using the baseline tissue specimen and explored in relation to 4-month progression-free survival and subsequently in relation to other clinical outcomes such as tumor response and adverse event incidence using two-way tables and analyzed using Fisher's exact tests. To estimate power for this primary analysis, we assume that 90% of patients (N=33) will provide a usable sample (i.e., will have gene amplification status for this tissue study). We also assume that 70% of patients (N=23) will have PKC1 gene amplification (Regala et al., 2005b) and that 55% of patients overall will have 4-month PFS. The proportion of patients with 4-month PFS will be compared between patients with tumors with PKC1 gene amplification to patients with tumors without PKC1 gene amplification using a 1-sided α =0.10 Fisher's exact test. We have 86% power to detect a 50% difference in the 4-month PFS rates (70% vs 20%) between gene amplified and gene not amplified groups (calculated using nQuery Advisor 6.01 with the following parameters: α =0.10 1-sided, π 1=0.70, π 2=0.20, n1=23, n2=10).

PKC1 protein expression (using the baseline tissue specimen) will be evaluated at baseline and explored in relation to clinical outcomes such as 4-month progression-free survival, tumor response, and adverse event incidence using two-way tables and box plots and analyzed using Fisher's exact tests or logistic regression methods, as appropriate. Further, the relationship among PKC1 gene amplification and PKC1 protein expression will be investigated using box plots and scatter plots and analyzed using Wilcoxon rank sum tests and Spearman correlation coefficients, as appropriate.

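### Section 17.3 relates the measured PRKCI copy number to 4-month PFS only as a yes/no cut, and its logistic model has no estimate if no marker-negative patient succeeds; add a numerical model and a small-sample fit

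*Combined protocol and SAP*

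**What the plan says.** Section 16.52 takes baseline PKC-iota gene amplification "to be the primary analysis (though still exploratory) among the" translational analyses. Amplification is a yes/no variable, set against 4-month PFS in a two-way table with a one-sided 0.10 Fisher's exact test. The power basis is 33 usable samples and a prevalence: "We also assume that 70% of patients (N=23) will have" amplification, which leaves 10 without. The result is "We have 86% power to detect a 50% difference in the 4-month PFS rates", that is "70% vs 20%) between gene amplified and gene not amplified groups". No copy-number threshold for amplification is given there.

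Section 17.3 describes the assay as a PRKCI copy number analysis. Copy number enters the 4-month PFS analysis as one binary predictor, at least one additional copy or not. It and each marker's "extra copy of the gene) and IHC scoring for the given marker will be evaluated using logistic regression models", one predictor per model, with an odds ratio and 95% confidence interval. The treatment of IHC differs: "For each marker, IHC scores will be considered as a numerical variable to assess" a linear association, and they are also split at the sample median. The Kaplan-Meier and Cox analyses at the end of 17.3 use the same predictors, so no analysis there uses the copy number as a number either.

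**The concern.** Copy number comes out of the assay as a quantity, and part of the biological rationale is graded. Section 1.21 says "We have demonstrated a correlation between the sensitivity of NSCLC cells to the anti-tumor effects of ATM, and the level of expression of" PKC-iota, and the marker background in section 1.3 names gene amplification as a major driver of that expression. A single low cut treats a tumor with one additional copy like a highly amplified one. The plan gives no reason for keeping IHC numerical and copy number not, in a sample of about 33 that cannot be enlarged for this question.

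The second issue is whether the promised result will exist. The marker-negative group is expected to hold about 10 patients, mostly failures. If none succeeds, ordinary logistic regression has no finite odds ratio and its Wald interval is unusable. Section 17.3 names no fallback.

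Section 16.52 intends these results to inform the design of later confirmatory studies, so what is lost here is lost to that design.

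**Working it through.** **Inputs.** From 16.52: 33 usable samples (0.90 × 37 = 33.3), 70% amplified (0.70 × 33 = 23.1, so 23 vs 10), success rates 70% and 20%, one-sided 0.10, Fisher. These fit the assumed 55% overall: (23 × 0.70 + 10 × 0.20)/33 = 18.1/33 = 0.548. From 17.3: the binary predictor, the logistic model and the 95% interval. The documents do not give the distribution of copy number or the shape of its effect, so both are assumptions below.

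**1. The plan's own power.** Exact power = Σ Bin(a; 23, 0.70) × Bin(b; 10, 0.20) over all outcomes (a, b) with a one-sided hypergeometric tail ≤ 0.10. Result: 0.868, against 86% stated. It reproduces.

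**2. Dependence on prevalence.** Same formula, rates held at 70% and 20%, 33 patients, split varied (assumed range):

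| Positive / negative | Share positive | Fisher power |
|---|---|---|
| 13 / 20 | 39% | 0.92 |
| 17 / 16 | 52% | 0.92 |
| 20 / 13 | 61% | 0.92 |
| 23 / 10 | 70% | 0.87 |
| 26 / 7 | 79% | 0.80 |
| 28 / 5 | 85% | 0.68 |

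Power can move either way.

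**3. Information lost by the split.** Assume copy number on a suitable scale (for example log2) is standard normal, x, with 70% above the cut, so the cut is at z = −0.524. For small effects, the efficiency of the split relative to the full scale is φ(z)²/[p(1−p)] = 0.3477²/(0.30 × 0.70) = 0.58.

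For effects of the planned size, simulate 33 patients with logit P(success) = α + βx. Choose α and β so that the average rates above and below the cut equal the stated pair. The score test is Z = r√(n−1), with r the correlation between predictor and outcome, rejecting at Z > 1.28. It is applied once to x and once to the yes/no split. The last row replaces the graded effect with a step at the cut. I used 60,000 simulated trials per row.

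| Scenario | Trend on x | Score test on split | Fisher on split |
|---|---|---|---|
| Graded, 70% vs 20% | 0.99 | 0.93 | 0.86 |
| Graded, 65% vs 32% | 0.85 | 0.69 | 0.54 |
| Pure step, 70% vs 20% | 0.78 | 0.93 | 0.86 |

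With no effect, the rejection rates are about 0.10, 0.10 and 0.05. The like-for-like cost of the split is therefore the second column against the third. The further drop to the Fisher column comes from that test's conservatism, not from the split. The 65% vs 32% scenario is an assumed smaller effect with the same overall rate (0.70 × 0.65 + 0.30 × 0.32 = 0.551).

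**4. Empty cell.** Under 16.52's own 20% in 10 patients, P(no success among marker-negative patients) = 0.80^10 = 0.107. The log odds ratio then has no finite maximum-likelihood value.

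**The case against.** The case against is substantial, and much of it stands.

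- **The 86%.** A reader might infer that the power is wrong or will not be delivered. Step 1 shows it is right on its inputs. The 70% matches a figure that section 1.31 gives for squamous tumors, where it says amplification is most prominent. Section 3.12 also admits Ras-mutated adenocarcinoma and small cell disease, so prevalence could fall below 70%, where power at the same rates is about 0.92.
- **The cut.** A reader might infer that one additional copy conflicts with amplification in 16.52. The marker background in section 1.3 uses copy number and amplification for the same measurement, so the natural reading is that 17.3 supplies the yes/no definition. What is missing is a cross-reference. No mismatch is shown.
- **Where the loss arises.** A reader might say that 17.3 degrades the lead analysis. That analysis is the Fisher test in 16.52, which is already binary and gives a valid p-value with an empty cell. The empty-cell problem belongs to the logistic model alone.
- **The hypothesis.** The graded statement in 1.21 concerns expression, and expression is analysed numerically through IHC. At the gene level, section 1.25 speaks of tumors with amplification, which suits a yes/no variable.
- **Replacing the binary test.** A reader might want the trend test to lead. Under a pure step it is clearly weaker (0.78 vs 0.93), and the documents do not say which shape holds.

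These points remove any claim of error in the power statement and any case for demoting the binary test. They do not explain why copy number alone has no numerical analysis against PFS, or what is reported when the odds ratio does not exist.

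**Conclusion.** The point holds as an inexpensive improvement to an exploratory analysis. Section 17.3 leaves measured information unused. If the effect is graded, power is about 0.99 vs 0.93 at 70% vs 20%, and 0.85 vs 0.69 at 65% vs 32%. These figures rest on an assumed normal scale, 70% above the cut and a logit-linear effect; under a step at the cut the ordering reverses. The chance of 0.107 that the marker-negative group has no success, leaving no finite odds ratio, rests only on 16.52's own rate and group size.

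The documents do not support calling the 86% wrong or showing that it would fall, and they do not show that the two sections use different cuts. The translational analyses are declared exploratory and unadjusted, and the 37-patient decision rule in 16.41 does not depend on them.

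**What to change.** 1. **16.52:** keep the binary one-sided 0.10 Fisher test as the lead exploratory marker analysis.
2. **17.3:** add a prespecified logistic model for 4-month PFS with copy number as a number (for example log2 copy number, one degree of freedom), beside the binary one, as is already done for IHC.
3. **17.3:** fit the logistic models by Firth's penalised likelihood with profile intervals, or by exact methods. Firth gives a finite estimate in both the binary and the numerical model. Exact conditional inference gives a valid interval for the binary predictor, but with an empty cell one limit is infinite, and it suits a continuous predictor poorly.
4. **Clarification only:** state the copy-number cut that defines amplification, use it in both sections, and fix it before marker data are linked to outcomes. Note that the 86% is conditional on 70% positive at that cut.

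The cost is a few sentences and one more model on data already produced. The downsides are an additional unadjusted exploratory result, and a numerical model that is weaker than the binary one if the effect is a pure step at the cut. That is why both are kept.
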